## 5 Planned Analyses

The following analyses will be performed for this study:

- Interim Analysis
- Final Analysis

### 5.1 Data Monitoring Committee (DMC)

There will be no DMC for this study.

### 5.2 Interim Analysis

A blinded interim analysis for sample size re-estimation will be conducted when approximately 50% of patients complete their mid-week treatment day dialysis session and corresponding  $\lambda$  FLC and  $\beta$ 2-MG RRs are available.

This interim analysis allows for modifying the sample size while the study is ongoing and is based on a blinded estimate of the variance. The one-sample estimator which will be calculated from the pooled data maintains trial integrity, shows good performance and is therefore recommended for application.

The data utilized during the interim analysis will be based on the FAS and statistics will be limited to the calculated one-sample variance estimator (not split by treatment group) of the  $\lambda$  FLC and  $\beta$ 2-MG RRs measured at the mid-week treatment day dialysis session. For sample size re-estimation, for each primary endpoint, the same sample size calculation as outlined in Section 3.2 will be carried out using the one-sample variance estimator which is based on the pooled variance (across both treatment groups) of the RRs as observed in the patients included in the interim analysis. In case the re-estimation for the sample size of  $\lambda$  FLC or  $\beta$ 2-MG yields a patient number  $> 272$  (including 5% drop out), the sample size of the study will be increased to this re-calculated number but will not exceed 350. In case the sample size reassessment for  $\lambda$  FLC or  $\beta$ 2-MG yields a patient number  $\leq 272$  (including 5% drop out), the sample size of the study will not be adjusted and the original sample size of 272 will be maintained. Due to this blinded and pooled (non-treatment group based) approach in re-estimation of the sample size and the absence of early stopping for futility and efficacy, no

alpha adjustment is required for the final analysis.

The steps of re-estimating the sample size are described as follows:

1. For each primary endpoint:
  - Regard the collected data (approximately 50% of all patients) as one sample, and estimate the mean and standard deviation (SD);
  - Based on a 1:1 randomization, use the normal approximation;
  - Use the one-sided significance level as 0.025 and the power of 90% to calculate the sample size;
2. Choose the larger re-estimated sample sizes of the two endpoints, and enlarge it with the 5% drop-off rate. If the re-estimate is smaller than 272, the study will stick on the original 272-sample design, and if the re-estimate is greater than 272, the new sample size will be used to recruit patients.
3. In case the re-estimation for the sample size of  $\lambda$  FLC or  $\beta 2$ -MG yields a patient number  $> 272$  (including 5% drop out), the sample size of the study will be increased to this re-calculated number but will not exceed 350. In case the sample size reassessment for  $\lambda$  FLC or  $\beta 2$ -MG yields a patient number  $\leq 272$  (including 5% drop out), the sample size of the study will not be adjusted and the original sample size of 272 will be maintained. Due to this blinded and pooled (non-treatment group based) approach in re-estimation of the sample size and the absence of early stopping for futility and efficacy, no alpha adjustment is required for the final analysis.

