## **8.11 Interim Analysis**

A blinded interim analysis for sample size re-estimation will be conducted when approximately 50% of patients complete theirmid-week treatment day dialysis session and corresponding  $\lambda$  FLC and  $\beta$ 2-MG RRs are available.

This interim analysis allows for modifying the sample size while the study is ongoing and is based on a blinded estimate of the variance. The one-sample estimator which will be calculated

---

from the pooled data maintains trial integrity, shows good performance and is therefore recommended for application [22].

The data utilized during the interim analysis will be based on the FAS and statistics will be limited to the calculated one-sample variance estimator (not split by treatment group) of the  $\lambda$  FLC and  $\beta 2$ -MG RRs measured at the mid-week treatment day dialysis session. For sample size re-estimation, for each primary endpoint, the same sample size calculation as outlined in Section 8.2 will be carried out using the one-sample variance estimator which is based on the pooled variance (across both treatment groups) of the RRs as observed in the patients included in the interim analysis. In case the re-estimation for the sample size of  $\lambda$  FLC or  $\beta 2$ -MG yields a patient number  $> 272$  (including 5% drop out), the sample size of the study will be increased to this re-calculated number but will not exceed 350. In case the sample size reassessment for  $\lambda$  FLC or  $\beta 2$ -MG yields a patient number  $\leq 272$  (including 5% drop out), the sample size of the study will not be adjusted and the original sample size of 272 will be maintained. Due to this blinded and pooled (non-treatment group based) approach in re-estimation of the sample size and the absence of early stopping for futility and efficacy, no alpha adjustment is required for the final analysis.

This interim analysis does not involve comparison of efficacy between groups, and will be performed by the sponsor or a Contract Research Organization (CRO) or a third party authorized by the sponsor. The details will be described in the Statistical Analysis Plan.

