## 3.2 Sample Size Calculation

### 3.2.1 Total Sample Size

The goal of this study is to demonstrate non-inferiority of Theranova 400 compared to FX 800 in the 2 primary endpoints and the non-inferiority margins selected are considered clinically acceptable. The sample size calculation is performed using PASS procedure Mann-Whitney U or Wilcoxon Rank-Sum Tests for Non-Inferiority. A separate sample size calculation is performed for both primary endpoints using a specified non-inferiority margin of 10% and a one-sided alpha level of 0.025, where the true difference in means is assumed to be zero (0).

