### 3.2.3 Sample Size Calculation In Regard To $\beta 2$ -MG Reduction Ratio

A previously conducted Theranova HDF study was used to obtain  $\beta 2$ -MG RR mean and SD of 78.48 and 6.75; a higher estimate for SD of 14.28 is used to calculate sample size to

account for a potential increase in variability based on a literature review of studies conducted in China. Based on a 1:1 randomization, with a sample size of 75 patients in the Theranova 400 group and 75 patients in the FX 800 group (total N = 150), a Wilcoxon Rank-Sum test  $\alpha$  with a 0.025 one-sided significance level will have 90% power to demonstrate non-inferiority of the Theranova 400 Dialyzer compared to the FX 800 Dialyzer as assessed by  $\beta 2$ -MG RR with a non-inferiority margin of 10% (i.e. 7.848).

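### Does the unnamed normal approximation in SAP 5.2 leave the re-estimated sample size open?

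*SAP*

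**What the plan says.** SAP 5.2 states that for each primary endpoint "the same sample size calculation as outlined in Section 3.2 will be carried out using the one-sample variance estimator". Protocol 8.11 says the same of its own section: "the same sample size calculation as outlined in Section 8.2 will be carried out using the one-sample variance estimator". The method meant is named in SAP 3.2.1: "The sample size calculation is performed using PASS procedure Mann-Whitney U or Wilcoxon Rank-Sum Tests for Non-Inferiority". For λ FLC that calculation uses SD 9.09 and margin 3.783 and gives 129 per arm. For β2-MG it uses SD 14.28 and margin 7.848 and gives 75 per arm. Allowing for 5% loss, 272 patients are randomised.

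The step list in SAP 5.2 then tells the analyst to treat the interim data as a single sample, to estimate its mean and SD, and: "Based on a 1:1 randomization, use the normal approximation". It adds one-sided 0.025 and 90% power, takes the larger of the two results and inflates it for 5% loss. The result sets recruitment: "if the re-estimate is greater than 272, the new sample size will be used to recruit patients". The next step caps it at 350.

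Two other places bear on the same figures. The synopsis gives 129 per arm and 90% power for λ FLC beside SD 8.26 alone. Protocol 10.2 speaks of about 308 valid cases.

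**The concern.** A re-estimation rule that sets recruitment should give one number whoever runs it. The step list is what a programmer would follow, and it does not say what is being approximated. The textbook normal formula for two means gives a smaller sample than the planned Wilcoxon method, so the trial might be enlarged too little, or not at all when the planned method would have enlarged it.

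The step list also asks for the mean, although the text above it limits the interim statistics to the variance estimator. Because the margins were derived as 10% of an assumed mean (protocol 8.5), a reader might ask whether the interim mean could move them. Finally, the synopsis power does not follow from the only SD printed there, and 308 matches neither 258 evaluable nor 272 randomised.

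**Working it through.** **Inputs.** One-sided alpha 0.025, power 90%, true difference 0 (SAP 3.2.1 and 5.2); the SDs and margins above (SAP 3.2.2, 3.2.3); 5% loss (SAP 3.2.4); floor 272 and cap 350 (SAP 5.2). (1.960 + 1.2816)² = 10.507.

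**1. The planned figures.** Take the smallest n per arm with exact t-test power of at least 90%, then multiply by π/3 = 1.0472, the efficiency factor of the Wilcoxon test for normal data.
- λ FLC: 123 × 1.0472 = 128.8, so 129.
- β2-MG: 71 × 1.0472 = 74.4, so 75.
- Inflation: 129/0.95 = 135.8, so 136 per arm and 272 in total.

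All three match the plan. The PASS setting is not shown, so this is a reconstruction.

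**2. Plain two-sample formula.** n = 2 × 10.507 × (SD/margin)².
- λ FLC: 2 × 10.507 × (9.09/3.783)² = 121.3, so 122 per arm; 122/0.95 = 128.4, so 129 per arm and 258 in total.
- β2-MG: 2 × 10.507 × (14.28/7.848)² = 69.6, so 70.

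Neither matches the plan.

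**3. Normal approximation to the Wilcoxon test, λ FLC.**
- Plain formula × π/3: 121.3 × 1.0472 = 127.1, so 128 per arm and 270 in total.
- Noether: n = 10.507 / [6(p − 0.5)²] with p = Φ(3.783/(9.09√2)) = 0.6157. This gives 130.8, so 131 per arm and 276 in total.

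The two variants sit on either side of the planned 272.

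**4. Randomised total after floor and cap, by interim λ FLC SD.**

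| SD | Planned method | Plain × π/3 | Noether | Plain |
|---|---|---|---|---|
| 9.09 | 272 | 272 | 276 | 272 |
| 9.2 | 278 | 276 | 284 | 272 |
| 9.3 | 286 | 280 | 290 | 272 |
| 9.5 | 298 | 294 | 302 | 280 |
| 10 | 328 | 326 | 334 | 310 |
| 10.7 | 350 | 350 | 350 | 350 |

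λ FLC governs: β2-MG would exceed 272 only above an SD of about 18.9, against 14.28 planned. The plain formula departs from the planned method for SDs of about 9.12 to 10.6, by at most 20 patients. The Wilcoxon variants stay within 8.

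**5. Power at the plain-formula size.** The primary analysis is a two-sample t-test (SAP 17.1.2). Its power comes from the noncentral t with noncentrality margin/(SD√(2/n)) and 2n − 2 degrees of freedom. At SD 10, 310 × 0.95/2 gives 147 evaluable per arm and a noncentrality of 3.783/(10√(2/147)) = 3.24; power is about 90%. It stays at about 90% across SDs 9.5 to 10.6. The Wilcoxon test would have about 88.5%.

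**6. Chance that the reading matters.** Take the interim SD as the true SD × √(χ²₁₃₅/135), for 136 patients, normal reduction ratios and no true difference. On the plain reading the final N differs, and the decision to enlarge differs, with these chances: 4% and 3% if the true SD is 8.26; 46% and 17% if it is 9.09; 77% and 8% if it is 10. With plain × π/3, the decision to enlarge differs with a chance of 1% to 3%; N itself may still differ, by a few patients.

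**7. Synopsis.** With 129 per arm and SD 8.26, power is 94.7% (Wilcoxon) or 95.6% (t-test), and 90% would need 107 per arm. With SD 9.09, as in protocol 8.2.1.1 and SAP 3.2.2, it is 90.2% or 91.5%.

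**The case for a change.** The strongest case for a change is that a pre-specified rule which fixes recruitment should not depend on who reads it. An analyst who followed only the step list and used the plain formula would, if the true SD is the planning value, reach a different N nearly half the time and a different decision to enlarge about one time in six. The wording that would settle it is a single phrase.

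What stands is that the bullet is loose. What does not stand is the step from there to a faulty plan. The large figures belong to a reading that contradicts the sentence opening the same procedure, which sends the analyst back to the Wilcoxon calculation. Even on that reading the shortfall hardly touches the primary test. The 88.5% concerns the Wilcoxon test, which is a sensitivity analysis in the SAP and, in the protocol, the fallback for non-normal data.

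The worry about the mean is speculative. An SD is computed around a mean, and a pooled blinded mean reveals no treatment difference. The margins are fixed numbers in protocol 8.5 and 8.7.1.1 and in SAP 17.1.2, and both documents say that the calculation is repeated with the variance estimator.

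**Conclusion.** No change to the plan follows. SAP 5.2 lacks a detail that an analyst can supply from the same section: the approximation is to the Wilcoxon test already used for planning, only the SD is updated, and the margins stay fixed. On that reading the re-estimated total is within about 8 patients of the planned method, in either direction. On the less natural plain reading it is at most 20 lower over a limited SD range, with about 90% power kept for the primary t-test and no effect on type I error.

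The missing SD 9.09 in the synopsis is a clerical omission. The protocol body and the SAP give it, and 129, 272 and 90% are correct there. The 308 sits in a feasibility narrative and enters no calculation.

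These sizes rest on normally distributed reduction ratios, no true difference between groups, and the π/3 reconstruction of the PASS procedure. The reconstruction reproduces both stated sample sizes, but the documents do not confirm it. A different rounding inside it moves N by 2 at some SDs.

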### **5.3 Final Analysis**

All final, planned analyses identified in this SAP will be performed by Kun Tuo Biostatistics following Sponsor Authorization of this Statistical Analysis Plan and Database Lock.

## **6 Analysis Sets**

Agreement and authorization of patients included/ excluded from each analysis set will be conducted prior to database lock.

### **6.1 Intention-To-Treat Full Analysis Set (FAS)**

Includes all randomized patients. Patient assignment will be based on the treatment randomized.

### **6.2 Per Protocol Set (PPS)**

PPS is a subset of the FAS and meets the following requirements: Patients were randomized to the respective treatment at the mid-week treatment day dialysis session and did not have any major protocol deviations that could affect the assessment of the primary endpoint when dividing the patient population.

Major protocol deviations when dividing the patient population are defined as follows:

- The actual QB of the patient is < 220 mL/minute for a duration of more than 30 min or for a total duration of > 60 minute at the mid-week treatment day dialysis session; patients in control group who actually do not achieve at least 16 L convective volume (including UF)
- The actual dialysis time of the patient is < 210 minute at the mid-week treatment day dialysis session.

### **6.3 Safety Set (SS)**

Includes all enrolled patients (ICF signed) that have been treated. Patient assignment will be based on actual treatment received.

## **7 General Considerations**

### **7.1 Reference Start Date And Study Day**

Study Day will be calculated from the reference start date, and will be used to show start/stop day of assessments and events.

Reference start date is defined as the day of the first application of study device and will appear in every listing where an assessment date or event date appears.

- If the date of the event is on or after the reference date then: Study Day = (date of event – reference date) + 1.
- If the date of the event is prior to the reference date then: Study Day = (date of event – reference date).

In the situation where the event date is partial or missing, Study Day, and any corresponding durations will appear partial or missing in the listings.

### **7.2 Baseline**

Unless otherwise specified, baseline is defined as the last non-missing measurement (including unscheduled assessments) taken prior to the first application of study device. In the case where Adverse Events (AEs) and medications without onset time record commencing on the reference start date will be considered post-baseline.

### **7.3 Retests , Unscheduled Visits and Early Termination Data**

In general, for by-visit summaries, data recorded at the nominal visit will be presented.

Unscheduled measurements will not be included in by-visit summaries.

In the case of a retest (same visit number assigned), the last available measurement for that visit will be used for by-visit summaries.

Data of 'early termination' visit will not be included in by-visit summaries.

Listings will include scheduled, unscheduled, retest and early discontinuation data.

### **7.4 Windowing Conventions**

No visit windowing will be performed for this study.

### **7.5 Statistical Tests**

Unless specified, all statistical tests will be performed at a significance level of 5% with two-sided 95% confidence interval (CI).

### **7.6 Common Calculations**

Descriptive statistics for continuous variables include number of cases, the number of missing cases, arithmetic mean, standard deviation, median, Q1, Q3, minimum, and maximum. Class variables will be described by frequency and percentage.

The level of precision for each continuous parameter statistic will be presented as follows:

- minimum/maximum in same precision as in the data or database, as appropriate,
- mean/median/Q1/Q3 in one more level of precision than minimum/maximum,
- SD in one more level of precision than mean/median,
- n will be presented as an integer.

For class variables, the percentage retains one decimal place. When the frequency is 0, the percentage will not be displayed; when the percentage is 100%, the percentage will be

displayed as 100%. If there is no special explanation, the denominator of the percentage is the number of cases in the corresponding analysis set. If there are missing values, the number of missing cases will be presented in a separate ‘missing’ line, unless otherwise specified.

For quantitative measurements, change from baseline will be calculated as:

- Test Value at Treatment Interval X – Baseline Value

## 7.7 Software Version

All analyses will be conducted using SAS version e.g. 8.2 or higher.

## 8 Statistical Considerations

### 8.1 Missing Data

For the primary efficacy endpoints, multiple imputation and tipping point analysis will be used to impute missing values of the  $\lambda$  FLC and  $\beta$ 2-MG RRs using the Intention-to-treat FAS for the sensitivity analysis. Imputation method are detailed in section 17.1.3.

No additional data will be imputed.

### 8.2 Multiple Comparisons / Multiplicity

The two primary endpoints will be tested simultaneously. Only when both primary endpoints pass is the study declared successful. Therefore, no multiplicity adjustment are necessary for this portion. Hierarchical structure will be used for the testing for both non-inferiority and superiority. Superiority will only be tested if non-inferiority passes.

There are no other multiplicity adjustments are made for the study. The secondary endpoint is not assigned to alpha, so it not refers to alpha adjustment. All secondary endpoints, all p values are descriptive in nature only.

## 9 Output Presentations

[Appendix 1](#) Partial Date Conventionsshow conventions for presentation of data in outputs.

The templates provided with this SAP describe the presentations for this study and therefore the format and content of the summary tables, figures and listings to be provided by Kun Tuo Biostatistics. All data collected will be listed. When the content of this SAP does not match the template, the template will take priority.

## 10 Disposition and Withdrawals

All patients who provide informed consent will be accounted for in this study.

Patient disposition and withdrawals including inclusion and exclusion criteria will be presented for all patients. The numbers and percentages of patients who were randomized, completed procedure within two weeks of randomization, completed and discontinued from the study will be summarized by treatment and overall. Reasons for discontinuation from the study will be summarized.

The numbers and percentages of patients in each analysis set will be provided by treatment group and overall. A listing of patients who are excluded from analysis sets, with reason for excluded from analysis set will be produced.

## **11 Protocol Deviations**

Any act of intentional or unintentional variation of the protocol is defined as protocol deviation (PD). The numbers and percentages of patients in the FAS with any protocol deviation will be summarized by treatment, deviation category and overall. All protocol deviations will be listed. Protocol deviations will be summarized by categories and overall.

## **12 Demographic and other Baseline Characteristics**

Demographic data and other baseline characteristics will be presented for Intention-to-treat FAS and be summarized by treatment and categories. A listing will be provided.

The following demographic and other baseline characteristics will be reported for this study:

- Age (years) ,defined as Age(Years)=(Date of signed ICF – Date of birth)/365.25, round down to integer
- Sex
- Child-bearing potential, only for female
- Ethnicity
- Dialysis Vintage (years)
- Weight (kg) at baseline
- Height (cm) at baseline
- BMI ( $\text{kg}/\text{m}^2$ ) at baseline, defined as  $\text{BMI} (\text{kg}/\text{m}^2) = \text{weight} (\text{kg})/\text{height} (\text{m})^2$

## **13 Renal Disease Baseline Characteristics**

Renal baseline characteristics will be presented for Intention-to-treat FAS and be summarized by treatment and categories. A listing will be provided.

- Renal diagnosis etiology
- Type of first chronic dialysis treatment
- Received Renal Transplantation

## **14 Previous Treatment Parameter**

Previous Treatment Parameter will be presented for Intention-to-treat FAS and be summarized by treatment and categories. The average over 6 times dialysis for continuous variables will be summarized by six previous treatment types. A listing will be provided using all data from the last 6 times.

The following previous treatment parameter will be reported for this study:

- Total duration of hemodialysis(years)
- Dialysis frequency in latest 6 times
- Total dialysis time(min)
- Dialyzer used
- QB(mL/min)
- QD(mL/min)
- Type of vascular access
- Treatment Type
- Scheduled replacement volume(L)
- Actual replacement volume(L)
- Treatment interruption, interruption time will also be summarized when treatment interruption exists.
- Anticoagulation Type,if having Anticoagulation,
- Anticoagulation supplement during the treatment, total supplement dose will also be summarized when anticoagulation supplement during the treatment exist.
- Dry weight(kg)

## **15 Medical History /Concomitant Illnesses**

SS will be used for Medical History/Concomitant Illnesses, unless otherwise specified. No inferential statistics will be provided.

- Medical History/Concomitant Illnesses will be coded using Medical Dictionary for Regulatory Activities (MedDRA XXX) terminology.
- Medical History are defined as those conditions prior to or at the day of the first application of study device.
- Concomitant Illnesses are conditions which started prior to the first application of study device and are ongoing after the first application of study device.
- Medical History/Concomitant Illnesses will be presented by primary system organ class (SOC) and preferred term (PT).

The illness will be regarded as concomitant Illnesses, if Medical History or Concomitant Illnesses cannot be classified according to the relationship between the date of the first application of study device and the start date of an illness.

